### **Prevention and treatment planning post-radiotherapy**

At each visit, patients will receive standardised oral hygiene and dietary advice (as above). Consultants will oversee treatment plans for the restoration of dental health. Required treatment will be co-ordinated by the School of Dentistry in line with current practice, including the possibility of routine treatment within primary care.

#### Extractions

The decision to undertake extractions should be taken after careful consideration of individual tooth prognosis, tooth abutment potential, the patient's medical history and other cancer related factors e.g. radiotherapy dose to mandible/maxilla. It is recommended that extractions be limited to teeth that are deemed unrestorable (see box below). All dental extractions should be undertaken in a hospital dental setting and following liaison with an Oral Surgery or Maxillofacial Surgery team.

#### UNRESTORABLE TEETH:

Subgingival caries/tooth margin >1mm

Periodontal pocket >5mm at one or more sites non-responsive to non-surgical periodontal treatment

Grade II mobile or worse

Apical pathology not responsive to orthograde root canal therapy

Root fracture/perforation/resorption

### **Clinical data transfer and storage**

Oral Health Assessment forms will be stored in each patient's clinical notes as they form an integral part of each patient's overall clinical assessment. Relevant anonymised data relating to dental caries, periodontal disease, saliva flow, and mouth opening will be transferred to a password-protected data spreadsheet on an encrypted password-protected Centre for Public Health, Queen's University computer. Information will be recorded alongside each patient's anonymous code. Please note the register of patients' Dental Health and H&C numbers and anonymous codes will be stored on a separate password-protected spreadsheet on a Belfast Health and Social Care Trust computer.

## **Radiation dose and tumour location determination**

Patients will receive radiotherapy as prescribed by their Consultant Clinical Oncologist. The Clinical Oncologist will also plan individual tissue exposures in line with current practice. There will be no alteration or experimentation with radiotherapy dose or the radiotherapy treatment plan for the purposes of conducting this research study.

Using additional research software (Non-Clinical Eclipse System by Varian Medical Systems UK Ltd), radiation dose exposures to the teeth and 'spared' parotid gland will be calculated after the teeth and parotid glands have been contoured on each patient's radiotherapy planning CT scan. The Clinical Oncologist will contour the parotid glands in line with current practice. A dentist will contour the teeth on patient-anonymised CT scans. Tumour location will be determined from the initial referral letter sent by the Head and Neck Cancer Multidisciplinary Team.

The dentist will be blinded to patient details when contouring teeth on CT scans. A 'unique identifier' will be generated for each patient's CT scan. A member of the clinical radiotherapy team (not involved in the study) will securely store a list of patients' 'unique identifiers' and H&C numbers on a Belfast Health and Social Care Trust computer. The dentist will then input radiation dose data (doses to the teeth and to the 'spared' parotid gland) alongside each patient's 'unique identifier' onto a separate password-protected spreadsheet stored on an encrypted password-protected Centre for Public Health, Queen's University Belfast computer.

## **Sample size**

Sample size calculations were conducted based upon an independent samples t-test and correlation coefficient. Assuming the standard deviation of the number of carious teeth in post-radiotherapy head and neck cancer patients is 4.0 (based upon the results of a 10-year School of Dentistry audit conducted by the applicant fellow) and comparing patients receiving over 20 Gray to the 'spared' parotid gland with those receiving under 20 Gray (based upon a 80%/20% distribution seen in the Cancer Centre radiation dose audit), we would require a total sample of 150 patients with available data to have over 80% power to detect a difference of 3.0 in the mean number of carious teeth between the under 20 Gy and over 20 Gy groups as statistically significant at the 5% level. Furthermore a sample size of 150 patients would allow 80% power to detect, as significant at the 5% level, a correlation coefficient of 0.22 for the association between radiation dose to the 'spared' parotid gland (Gy) and the number of carious teeth. Assuming 30% dropout we would therefore need to recruit 215 patients.

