## **Statistical analysis**

Primary outcome measures to be analysed include: (1) the number of carious teeth and (2) the presence of periodontal disease.

(1) Initial comparisons between the radiation dose to the 'spared' parotid gland and the number of carious teeth will be performed using independent t-tests (categorising radiation dose as <20Gy and >20Gy) and ANOVA (categorising radiation dose as <20Gy, 20-30Gy, 30-40Gy, and >40Gy) as appropriate. Adjusted analysis will be performed using multiple linear regression, with the number of carious teeth as the outcome variable, radiation dose to the 'spared' parotid gland as an explanatory variable

(categorised as above) along with potential confounding variables: dental radiation dose, oral hygiene practice, diet, and mouth opening. Without categorising radiation dose, a separate analysis will be conducted using linear regression with the number of carious teeth as the outcome variable and radiation dose to the 'spared' parotid gland (Gy) as the explanatory variable to give the increase in the number of carious teeth per 10 unit increase in Gray. If the number of carious teeth is not normally distributed transformations will be used prior to analysis or equivalent non-parametric techniques will be used.

(2) Initial comparisons of the association between radiation dose to the 'spared' parotid gland (categorised as above) and the presence of periodontal disease (Yes/No) will be performed using chi-square tests. Adjusted analysis will be performed using logistic regression with presence of periodontal disease as the outcome variable, radiation dose to the 'spared' parotid gland as the explanatory variable and dental radiation dose, oral hygiene practice, diet, smoking, medical history, and mouth opening as potential confounders.

Similar analyses will be undertaken to determine the effects of dental radiation dose and tumour location on the number of carious teeth and the presence of periodontal disease in post-radiotherapy head and neck cancer patients.

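### The 80% power stated for a correlation of 0.22 with 150 patients is slightly optimistic: at two-sided 5% it is about 77–78%

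*Combined protocol and SAP*

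**What the plan says.** The Sample size section rests on two calculations: "Sample size calculations were conducted based upon an independent samples t-test and correlation coefficient". The first compares mean numbers of carious teeth between patients above and below 20 Gy to the spared parotid, split 80%/20%, with a difference of 3.0 and a standard deviation of 4.0. It claims over 80% power with 150 patients who have data. The second says that "a sample size of 150 patients would allow 80% power to detect, as significant at the 5% level, a correlation coefficient of 0.22", the correlation being between spared-parotid dose in Gy and the count of carious teeth. The section then allows for losses: "Assuming 30% dropout we would therefore need to recruit 215 patients". It does not state sidedness, formula or software for either calculation.

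The matching analysis is in the Statistical analysis section, where dose is left uncategorised: "a separate analysis will be conducted using linear regression with the number of carious teeth as the outcome variable", with parotid dose as the explanatory variable and the result expressed per 10 Gy.

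**The concern.** The second calculation gives sample size, power, significance level and effect size, so it can be checked without any outside figure. The usual two-sided test of a correlation of 0.22 needs more than 150 patients for 80% power.

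This is the only power statement for continuous dose. It supports the per-10-Gy regression on a primary outcome and the parotid-dose part of the primary hypothesis. It is also the tighter of the two calculations, because the t-test comparison has power to spare. If it is optimistic, the plan claims slightly more sensitivity for this analysis than 150 patients provide.

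**Working it through.** **Inputs (Sample size section):** n = 150 with data; r = 0.22; significance level 5%; stated power 80%; dropout 30%. **Assumption:** two-sided test, since sidedness is not given; one-sided is tried below.

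**1. Power at r = 0.22, n = 150.**

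- Fisher's z: power = Φ(atanh(r)·√(n − 3) − 1.960). Here atanh(0.22) = 0.2237 and √147 = 12.124, so the product is 2.712 and power = Φ(0.752) = 77.4%.
- Simulation of 200,000 bivariate normal samples: 77.6%. The exact bivariate normal distribution of r gives 77.7%.
- Slope t-test with dose fixed: noncentrality = r/√(1 − r²)·√n = 0.2255 × 12.247 = 2.762. With 148 degrees of freedom and critical value 1.976, power = 78.4%.
- Large-sample version of the slope test: Φ(2.762 − 1.960) = 78.9%. This is the most favourable two-sided variant tried.

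**2. Evaluable patients needed for 80% power at r = 0.22.**

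- Fisher's z: ((1.960 + 0.8416)/0.2237)² + 3 = 159.9, so 160. The exact distribution gives 159.
- Slope t-test, dose fixed: 157. The large-sample slope version gives 155.

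**3. Correlation detectable with 80% power at n = 150.** This is the direction in which the section's sentence reads.

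- Fisher's z: tanh(2.8016/√147) = tanh(0.2311) = 0.227. The exact distribution gives 0.226. Both print as 0.23.
- Slope t-test, dose fixed: 0.2244. The large-sample slope version gives 0.223. Both print as 0.22.

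**4. One-sided test.** Fisher's z gives 85.7% power at n = 150 and needs 127 patients for 80%, so a one-sided 5% level does not explain the figure.

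**5. Value for a restatement.** At r = 0.23 and n = 150, Fisher's z gives 81.0% and the exact distribution 81.3%.

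**6. The gap in teeth.** With the section's standard deviation of 4.0, the slope per one standard deviation of dose is r × 4.0: 0.22 × 4.0 = 0.88 teeth against 0.227 × 4.0 = 0.91. The documents give no standard deviation for parotid dose, so this cannot be turned into teeth per 10 Gy.

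**7. The rest of the section.** For 30 against 120 patients, a difference of 3.0 and a standard deviation of 4.0, the noncentrality is 3.0/(4.0·√(1/30 + 1/120)) = 3.67. Power is about 95%, so the t-test statement holds. 150/0.7 = 214.3, so 215 is also correct.

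**The case against.** The strongest reply is that sample size and power are the inputs in this sentence and the correlation is a rounded output. The 150 already stands in the t-test sentence, and the next one asks what else that number can detect. The fair check is then whether the detectable correlation rounds to 0.22. Under the fixed-dose slope test it does (0.2244), and that test matches the planned linear regression. In simple regression the t-test of the slope and the t-test of the correlation are the same test; the power formulas differ only in whether dose is treated as fixed or random. On this view, solving for power at exactly 0.22 turns a third-decimal rounding into an apparent shortfall. The outcome is also a count that may be transformed, so no normal-theory power figure is accurate to two points.

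Much of this stands. A reader might infer that the figure is simply wrong and that no standard formula produces it. The documents do not support that, because a slope-type calculation prints as 0.22.

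Two things remain. The section names a correlation coefficient as its basis, and dose here is observed: the section on radiation dose and tumour location determination says that treatment plans are not altered for the study. The random-dose calculation is therefore the natural one, and it gives 0.227. Also, rounding a detectable effect downward overstates sensitivity, and no two-sided variant tried gives a full 80% at 0.22 with 150 patients.

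**Conclusion.** The statement is slightly optimistic. At two-sided 5%, 150 patients give about 77–78% power for a correlation of exactly 0.22, a shortfall of about 2 to 3 percentage points, or roughly 7 to 10 evaluable patients (157 to 160 against 150). The correlation detectable with 80% power is 0.227 on the named basis and 0.224 if dose is treated as fixed. These figures assume a two-sided test, normal-theory formulas and 150 patients with data.

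A reader might also infer that the study is underpowered or that recruitment must rise. Holding rigidly to 80% at 0.22 on the Fisher's z basis would mean 160/0.7 = 228.6, or 229 recruits. The documents do not require this: they give no reason why 0.22 rather than 0.23 is the correlation that matters, and the t-test comparison has about 95% power. The error lies in the wording of the claim, and the design can stay as it is.

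**What to change.** Replace the correlation sentence with one to this effect: *150 patients give at least 80% power (two-sided 5%) for a correlation of 0.23 between spared-parotid dose and number of carious teeth, and about 77–78% power for 0.22.* Name the formula used (Fisher's z, or a slope t-test with dose fixed). If the authors used a slope-type calculation, they should say so and give the detectable correlation to three decimals.

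The cost is one sentence and a marginally less favourable figure. Recruitment of 215, the t-test calculation and the planned analyses do not change.

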## **Statistical analysis**

Primary outcome measures to be analysed include: (1) the number of carious teeth and (2) the presence of periodontal disease.

(1) Initial comparisons between the radiation dose to the 'spared' parotid gland and the number of carious teeth will be performed using independent t-tests (categorising radiation dose as <20Gy and >20Gy) and ANOVA (categorising radiation dose as <20Gy, 20-30Gy, 30-40Gy, and >40Gy) as appropriate. Adjusted analysis will be performed using multiple linear regression, with the number of carious teeth as the outcome variable, radiation dose to the 'spared' parotid gland as an explanatory variable

(categorised as above) along with potential confounding variables: dental radiation dose, oral hygiene practice, diet, and mouth opening. Without categorising radiation dose, a separate analysis will be conducted using linear regression with the number of carious teeth as the outcome variable and radiation dose to the 'spared' parotid gland (Gy) as the explanatory variable to give the increase in the number of carious teeth per 10 unit increase in Gray. If the number of carious teeth is not normally distributed transformations will be used prior to analysis or equivalent non-parametric techniques will be used.

(2) Initial comparisons of the association between radiation dose to the 'spared' parotid gland (categorised as above) and the presence of periodontal disease (Yes/No) will be performed using chi-square tests. Adjusted analysis will be performed using logistic regression with presence of periodontal disease as the outcome variable, radiation dose to the 'spared' parotid gland as the explanatory variable and dental radiation dose, oral hygiene practice, diet, smoking, medical history, and mouth opening as potential confounders.

Similar analyses will be undertaken to determine the effects of dental radiation dose and tumour location on the number of carious teeth and the presence of periodontal disease in post-radiotherapy head and neck cancer patients.

Secondary outcomes to be analysed include: quality of life, salivary flow rate, diet, oral hygiene practice, mouth opening, xerostomia (all change from baseline); tooth loss, and denture wear. Dichotomous outcomes will be analysed using chi-square tests and logistic regression as above. Continuous outcomes will be analysed as above, apart from variables with baseline measurements, for which ANCOVA will be used to compare outcome measurements adjusting for baseline. Adjusted analyses will use multiple linear regression models as above but with baseline measurements as an additional explanatory variable.

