Patients will be asked to refrain from smoking, eating and drinking, and other forms of oral stimulation (e.g. oral hygiene) 90 minutes prior to the collection of saliva. It is anticipated that the length of each patient's pre-radiotherapy dental assessment will be at least 90 minutes (based on current clinical practice). Patients will therefore be instructed not to engage in oral stimulation for 90 minutes after they have signed the written consent form at the start of the appointment.

-Ruler measurement of **mouth opening**. Maximum interincisal distance will be measured when the upper and lower central incisors are present (natural or prosthetic). Alternatively, the alveolar ridge(s) will be used as a reference point for measurement where no natural or prosthetic central incisors are present.

All of the above data, including the Oral Health Assessment Forms, will be recorded and stored in patients' clinical records (dental notes).

**-Oral hygiene practice and dietary assessments** will be performed using the World Health Organization's Oral Health Questionnaire for Adults.

**-Quality of life** and experience of **xerostomia** will be assessed using questionnaire booklets containing the European Organization for Research and Treatment of Cancer (EORTC) QLQC30 quality-of-life instrument, the associated head and neck specific module HN35, the Oral Health Impact Profile, and the modified Xerostomia Questionnaire.

**-Micro-costings study.** Patients will also be asked to complete a short questionnaire enquiring of their gross annual income, the mode of transport they used for attending their dental appointment, and whether another person accompanied them to their dental appointment. The micro-costings study questionnaire will be attached to the oral hygiene/diet/quality of life/xerostomia questionnaire booklet outlined above.

The questionnaire booklets will be completed anonymously. Upon acceptance into the study, a random number generator will assign each recruited patient a 6-digit anonymous code. Each patient will be informed of his or her anonymous code. This will be the only identifier recorded on completed questionnaire booklets.

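### Age, sex and socioeconomic position are in neither primary adjustment list, so the adjusted parotid-dose associations may carry residual confounding of unknown size

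*Combined protocol and SAP*

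**What the plan says.** All references are to the combined protocol and SAP.

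- **Statistical analysis, item (1), caries.** The multiple linear regression has categorised spared-parotid dose as the explanatory variable, "along with potential confounding variables: dental radiation dose, oral hygiene practice, diet, and mouth opening". A separate regression on continuous dose, reported per 10 Gy, names no covariates.
- **Statistical analysis, item (2), periodontal disease.** The logistic regression has spared-parotid dose as the explanatory variable, with "dental radiation dose, oral hygiene practice, diet, smoking, medical history, and mouth opening as potential confounders".
- Neither list is worded as a set of examples. Age, sex and socioeconomic measures do not appear elsewhere in the analysis text.
- **Radiation dose and tumour location determination.** The oncologist plans tissue exposures under usual practice, and the study does not alter them.
- **Clinical assessment, micro-costings study.** Patients complete a short questionnaire "enquiring of their gross annual income". The Micro-costings analysis section gives its purpose as describing each patient's economic burden.
- **Clinical data transfer and storage; Spreadsheets.** The anonymised clinical files hold caries, periodontal, saliva and mouth-opening data, and the second section adds questionnaire results. Age and sex are not among the listed fields. A separate list held by the Trust links each anonymous code to the patient's Dental Health and H&C numbers.

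**The concern.** This is a prospective cohort in which patients are not allocated to a parotid dose, so the adjusted estimate is the main protection against confounding. Age and sex are the first patient characteristics a reader will look for in such a model, and the plan neither includes them nor explains leaving them out.

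Three features of the design give the omission some weight:

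- Eligibility is any adult with at least six teeth and no upper age limit, so age may vary widely.
- The periodontal definition includes attachment loss, which can predate radiotherapy. Neither primary model has a baseline disease term; baseline adjustment is planned only for secondary outcomes.
- Tumour location is analysed as an exposure in its own right and is not named as a covariate in the parotid-dose models. Any age or sex difference that runs through tumour site is therefore not picked up indirectly.

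If age or sex is related to both dose and outcome, the reported dose association would be partly theirs. Because the two fields are not in the listed data, an analyst following the plan might not have them to hand.

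**Working it through.** **1. The two lists side by side**

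| Variable | Caries model | Periodontal model |
|---|---|---|
| Dental radiation dose | yes | yes |
| Oral hygiene practice | yes | yes |
| Diet | yes | yes |
| Mouth opening | yes | yes |
| Smoking | no | yes |
| Medical history | no | yes |
| Age, sex, socioeconomic measure | no | no |

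**2. The plan's own sample size figures.** The inputs from the Sample size section are: "the standard deviation of the number of carious teeth in post-radiotherapy head and neck cancer patients is 4.0"; a split "based upon a 80%/20% distribution seen in the Cancer Centre radiation dose audit"; "a total sample of 150 patients with available data", hence 30 and 120; "over 80% power to detect a difference of 3.0 in the mean number of carious teeth"; and "as statistically significant at the 5% level". The section does not state sidedness, so I assume two-sided tests.

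- Recruitment: 150/(1 − 0.30) = 214.3, rounded up to 215. This reproduces.
- Standard error of the difference: 4.0 × √(1/30 + 1/120) = 0.816. Noncentrality: 3.0/0.816 = 3.67. With 148 df, power is 95.5%, which agrees with the statement of over 80%.

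Neither figure depends on the covariate list. They serve as the baseline for costing the fix.

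**3. Cost in the caries model.** Count the four listed covariates as one df each, and age and sex as two more, giving six adjustment df and 150 − 2 − 6 = 142 residual df.

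- If the covariates are unrelated to dose group, power is 95.4%, against 95.5% with none.
- If the six together explain a share R² of the variance in dose group, the standard error is divided by √(1 − R²). Assuming R² = 0.10 gives 93.3%, and 0.30 gives 86.3%, with no gain in outcome precision assumed.
- For a partial correlation of 0.22, power = Φ(atanh(0.22) × √(150 − 3 − k) − 1.96), where k is the number of covariates. This gives 76.3% at k = 4 and 75.7% at k = 6.

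**4. Cost in the periodontal model.** The documents give no prevalence. Assume 20% to 40% of 150, which is 30 to 60 cases. Assume also that the listed terms use 7 to 9 df once dose and medical history are coded.

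- As listed: 30/9 = 3.3 to 60/7 = 8.6 cases per df.
- With age and sex (9 to 11 df): 30/11 = 2.7 to 60/9 = 6.7.

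**5. What the bias could be.** For one omitted factor in a linear model, bias = (teeth per SD of the factor) × (SD imbalance between dose groups). The documents supply neither input. Assuming 0.5 to 1.5 teeth per SD and an imbalance of 0 to 0.5 SD:

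- smallest: any effect × 0 = 0 teeth;
- largest: 1.5 × 0.5 = 0.75 teeth, or 0.75/3.0 = 25% of the design difference.

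The result is exactly zero when the imbalance is zero, however strongly the factor affects caries.

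**The case against.** The strongest reply is that a variable confounds only if it is related to exposure as well as outcome, and nothing in the documents links age, sex or income to parotid dose. They say only that oncologists plan exposures in the usual way. A reader might infer that both dose associations are confounded, and avoidably so. The documents do not support that: they establish the omission, not the bias. This part of the objection stands in full.

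A reader might also try to size the problem by assuming an age gap between dose groups and an odds ratio per decade. For example, with a 5-year gap and odds rising 1.3-fold to 2.0-fold per 10 years, the multiplier on the dose odds ratio is 1.3^−0.5 = 0.88 to 2.0^−0.5 = 0.71, or the inverse in the other direction. Both inputs are invented for the purpose. The calculation covers only age and periodontal disease, and it ignores the covariates already in the model. It is not evidence of size.

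Three further points stand in part:

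- Oral hygiene and diet in both models, and smoking in the periodontal model, may absorb some of any socioeconomic effect. They do not stand in for age or sex.
- Pre-radiotherapy treatment is meant to leave patients free of dental disease, and the periodontal definition requires pocketing as well as attachment loss. Some accumulated disease is therefore removed before exposure. Not all need be: the extraction table is aimed at pockets above 5 mm and bone loss above 50%, so lesser attachment loss can persist.
- Income is self-reported and may be missing for some patients. That is a good reason not to make it a compulsory term in the primary models.

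**Conclusion.** The point holds in a limited form. Both primary adjustment lists omit age, sex and any socioeconomic measure, without a stated reason, in a study where dose is not randomised. The adjusted associations may therefore carry residual confounding. Its direction and size cannot be derived from the documents, and the 0 to 0.75 teeth above only shows how the answer moves with assumed inputs.

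The case for acting rests on the low cost, not on a demonstrated bias. In the caries model, adding age and sex leaves power for 3.0 teeth at about 95% if the covariates are unrelated to dose group, and at 86.3% if together they explain an assumed 30% of its variance. The firm recommendation covers age and sex only. Income as a main-model covariate and a compulsory penalised fit are both matters of judgement.

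**What to change.** 1. In Statistical analysis, items (1) and (2), add age (continuous) and sex to the covariates of both adjusted primary models before any outcome data are analysed.
2. In Clinical data transfer and storage, and in Spreadsheets, add age and sex to the anonymised clinical dataset. Obtain them from the clinical record through the existing list linking anonymous codes to Dental Health and H&C numbers.
3. Prespecify a sensitivity analysis that adds baseline gross annual income to both models and reports how many patients have it missing. The item is already in the questionnaire booklet, and questionnaire results are filed under the same anonymous code as the clinical data.
4. For the periodontal model, state that a penalised logistic fit (for example Firth's) may be used if cases are few.

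**Cost.** A sentence or two in the analysis section, two extra data fields with the matching change to the data-transfer text, and about two degrees of freedom. The loss is negligible in the caries model. In the logistic model, under the assumed 30 to 60 cases, it lowers cases per df from roughly 3.3–8.6 to 2.7–6.7.
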